8.5 Sample Size and Power

A minimum sample size of 1250 subjects will be randomized in the trial up to a maximum of 1550 randomized subjects.

[REDACTED]

[REDACTED]

- [REDACTED]
- [REDACTED]
- [REDACTED]
- [REDACTED]

[REDACTED]

[figure not shown]
[Redacted text block]

[Redacted text block]

[Redacted text block]

[Redacted text block]

[Large redacted text block]

[Redacted text block]

[Large redacted text block]

8.6 Multiplicity Adjustment

The trial will be considered successful if both the primary effectiveness and primary safety endpoints are met. [Redacted]

[Redacted text block]

[REDACTED]

[REDACTED]

[REDACTED]

[REDACTED]

[REDACTED]

8.7 Additional Endpoints

A number of descriptive effectiveness and safety endpoints are included in this trial, and will be summarized by randomized arm (WaveCrest or control). [REDACTED]

[REDACTED] Summary statistics and 95% confidence intervals will be provided, and p-values will be provided as a descriptive measure of difference between the treatment groups, though no labeling indications will be sought for any of these endpoints.

8.7.1 Descriptive Safety Endpoints

Descriptive safety endpoints will be summarized and presented as detailed below.

- **Components of the primary safety composite endpoint**

The number and percentage of subjects who experience each component of the primary safety endpoint through 45 days will be presented.

- **Stroke (all types) or pericardial effusion**

The number and percentage of subjects who experience a stroke (ischemic, hemorrhagic, or indeterminant) or pericardial effusion through 45 days post-procedure

- **Pericardial effusion requiring surgical drainage**

The number and percentage of subjects who undergo pericardial effusion requiring surgical drainage through 7 days post-procedure or at hospital discharge, whichever is later, will be presented by intervention type (surgical vs. percutaneous).

- **All-cause mortality**

Event rates per subject-year for all-cause mortality will be estimated assuming a one-parameter exponential survival model. [REDACTED]

- **Cardiovascular mortality**

Event rates per patient-year for cardiovascular mortality will be estimated assuming an exponential survival model. [REDACTED]

- **Adverse events**

Adverse events (AEs) reported during the study will be coded using the Medical Dictionary for Regulatory Activities (MedDRA). The number and percentage of subjects reporting adverse events will be summarized by MedDRA system organ class and preferred term by treatment group and in total. Separate summaries will also be provided for device-related AEs and procedure-related AEs. [REDACTED]

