## 2.7 Clinical Experience with the WaveCrest Device

The WaveCrest device was studied in the Coherex WAVECREST 1 Left Atrial Appendage (LAA) Occlusion Study (WAVECREST 1 Study). One-hundred fifty-five (155) subjects were treated with the WaveCrest LAA occlusion device at 19 investigational sites in Europe, Australia and New Zealand. Three device versions were studied: **Version 1.1** (N=9), **Version 1.2** (N=73), **Version 1.3** (N=73). The study enrolled elderly subjects with an average CHADS2 Score of 2.5 and at high risk of stroke. More than half (65%) of enrolled subjects were contraindicated for anticoagulation. Clinical results on device **Version 1.3** are as follows: procedural success was achieved in a majority of subjects (96%). Procedure duration averaged 68 minutes, with 47% requiring no device repositioning. On average, 1.3 devices were used (i.e., attempted) per subject. At 45 days, LAA closure, defined as residual gap ≤3mm, occurred in 97% of subjects. With LAA closure defined as a residual gap ≤5mm, LAA closure at 45 days was 100%. Pericardial effusions/tamponade occurred at a rate of 2.7%, none requiring surgical intervention, and there were no unanticipated adverse events or unanticipated adverse device effects.

The WaveCrest device received the CE Mark in August 2013 and was available commercially in Europe in October 2013. Procedural success was high during limited market release, with 88/92 (96%) successful implants as of July 2014. Pericardial effusions occurred at a rate of 3.3% (3/92). There was one device embolization (1.1%). In 2 subjects (2.2%), a thrombus was discovered on a follow-up TEE. There were no procedural strokes. In 2 subjects, there was damage to the inner liner of the sheath - both cases were “incidents” as defined by MEDDEV 2.12-1 Rev 8 and warranted a Field Safety Notice (FSN) and Field Safety Corrective Action (FSCA) in Aug 2014. A FSCA has resulted in modification to the Delivery Sheath liner. The device is described in **Section 5**. The related Change Notification was reviewed and approved July 29, 2015 and commercial use outside the United States resumed in September 2015.

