**Descriptive Safety Endpoints**

The following safety endpoints will be descriptively summarized:

- Components of the primary safety composite endpoint through 45 days post-procedure
- The rates of stroke (all types) or pericardial effusion through 45 days post-procedure
- Pericardial effusion requiring surgical drainage through 7 days post-procedure or at hospital discharge, whichever is later
- Device- or procedure-related Serious Adverse Events (SAEs) reported by site at 45 days, 6 months, and at each annual follow-up period
- All-cause mortality at the time of primary analysis, at each annual follow-up period after the primary analysis, and at the end of trial follow-up (5 years)
- Cardiovascular mortality at the time of primary analysis, at each annual follow-up period after the primary analysis, and at the end of trial follow-up (5 years) - see definition in **Appendix I: Acronyms and Definitions**

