Type 3c	Intracranial hemorrhage (does not include microbleeds or hemorrhagic transformation, does include intraspinal) Subcategories confirmed by autopsy or imaging or lumbar puncture Intraocular bleed compromising vision
Type 4	CABG-related bleeding - Perioperative intracranial bleeding within 48 h Reoperation after closure of sternotomy for the purpose of controlling bleeding Transfusion of $\geq 5$ U whole blood or packed red blood cells within a 48-h period† Chest tube output $\geq 2\text{L}$ within a 24-h period
Type 5	Fatal bleeding
Major Vascular Complication	Access site or access-related vascular injury (dissection, stenosis, perforation, rupture, arteriovenous fistula, pseudoaneurysm, hematoma, irreversible nerve injury, compartment syndrome, percutaneous closure device failure) leading to death, life-threatening or major bleeding, visceral ischemia, or neurological impairment
Pericardial Effusion (PE)	The presence of an abnormal or unexpected amount ( $>10\text{mm}$ ) of fluid or air in the pericardial space identified using echocardiography as echo-free space between the epicardium and parietal pericardium throughout the cardiac cycle. For the purposes of this study, PEs must include one or more of the following: 
 
1) Be accompanied by chest pain or other clinical symptoms (see definition of Cardiac Tamponade)
 
2) Have an increase of <math>>10\text{mm}</math> from baseline in either the width (circumferential) or largest measured dimension (loculated) by echocardiographic imaging
 
3) Require percutaneous or surgical drainage
 
 Pericardial effusions can be further characterized as follows: 
 
- Onset: Acute (intra-procedural), Subacute (post-procedure – 60 days), Long-term (<math>>60</math> days)
 
- Size: Mild (<math>\leq 10\text{mm}</math>), Moderate (11-20mm), Large (<math>>20\text{mm}</math>)
 
- Distribution: Circumferential or Loculated
 
- Hemodynamics: With or without Cardiac Tamponade or Effusive-Constrictive
 
- Type: Transudate, Exudate, Hydropericardium (transudate, plasma ultrafiltrate), Hemopericardium (blood in pericardial space), Chylopericardium (chylous pericardial fluid), Pyopericardium (purulent pericardial effusion), or Pneumopericardium (air in the pericardium)
 

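### Two descriptive pericardial effusion endpoints contradict themselves: a surgical-drainage count is to be split by surgical and percutaneous intervention, and the 10 mm threshold in the effusion definition conflicts with its own size classes

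*SAP*

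**What the plan says.** **The drainage item.** The protocol lists, in the synopsis and again in section 15.6, "Pericardial effusion requiring surgical drainage through 7 days post-procedure or at hospital discharge, whichever is later". It counts surgical drainage only and gives no split. SAP 8.7.1 keeps that population, "The number and percentage of subjects who undergo pericardial effusion requiring surgical drainage through 7 days post-procedure or at hospital discharge, whichever is later", and in the same sentence adds that it "will be presented by intervention type (surgical vs. percutaneous".

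**The definition of effusion.** The Appendix I entry opens with "The presence of an abnormal or unexpected amount" of fluid or air, with more than 10 mm given in parentheses. It continues: "For the purposes of this study, PEs must include one or more of the following". The three qualifiers are chest pain or other clinical symptoms, an increase of more than 10 mm from baseline, and "Require percutaneous or surgical drainage". The entry then grades size as *Mild* (10 mm or less), *Moderate* (11 to 20 mm) or *Large* (over 20 mm).

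**Where the term is used.** It underlies the drainage item and the descriptive rate of stroke or pericardial effusion through 45 days (protocol 15.6, SAP 8.7.1).

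**The concern.** Effusion is a recognised procedural hazard of these devices. Protocol 3.2 lists fewer effusions needing surgery as a possible WaveCrest benefit. The one endpoint devoted to drained effusions should therefore say clearly what it counts, and it does not. One programmer would deliver an empty percutaneous row. Another would take the display as the intention and add catheter-drained cases. The two tables would differ, and neither choice would break the SAP as written.

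The definition raises the same problem. Someone applying its opening clause would discard a small effusion that was symptomatic or had been drained. Someone applying the size classes would keep it and grade it *Mild*. If these questions are settled only when the tables are made, the reported effusion counts depend on a choice that nobody specified in advance.

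**Working it through.** No stated figure in the plan is in dispute, so the check is mainly a comparison of texts.

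**1. Can the split be filled?** The population is effusions drained surgically. The display has two rows, surgical and percutaneous. An effusion drained only by catheter is outside the population, so the percutaneous row has no eligible members.

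Other visible outputs that could hold these cases:
- The table of primary safety components through 45 days includes interventions. SAP 8.2.1 expects these to combine effusion or tamponade with vascular repair and device retrieval.
- The 45-day stroke-or-effusion rate combines effusion with stroke.
- The adverse event tables are by MedDRA class and term, not by type of drainage.

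None of them isolates catheter-drained effusions by arm. Redacted SAP text may add detail, but it cannot make the quoted sentence consistent.

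**2. What does the threshold do?** Let *s* be the current size, *b* the baseline size (*b* ≥ 0), both in mm in the same dimension. Read literally, an effusion counts if

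*s* > 10 **and** (symptoms **or** *s* − *b* > 10 **or** drained).

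- If *s* − *b* > 10 and *b* ≥ 0, then *s* > 10 already. The threshold adds nothing to the growth criterion.
- The rule therefore reduces to: *s* − *b* > 10, **or** [*s* > 10 and (symptoms or drained)].
- What the threshold removes is exactly the set with *s* ≤ 10 and symptoms or drainage.
- The *Mild* class is *s* ≤ 10. No qualifying effusion can fall in it.

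The *Mild* class therefore has a use only if some effusions of 10 mm or less count. Echocardiographic exclusion 4 (protocol 4.4.3) points the same way: it uses a 10 mm limit for circumferential and loculated effusions but treats a symptomatic effusion as relevant whatever its size.

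**3. Does it reach the primary endpoint?** Protocol 4.3.1 counts procedure- or device-related complications needing percutaneous or surgical intervention through 45 days. It names effusion drainage as an example and sets no size limit. Cardiac tamponade is also a Type 3b major bleed in Appendix I, and the tamponade entry has no minimum size. The primary composite is therefore not shown to be affected.

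**4. Scale.** Inputs: effusion rates of 2.7% (Version 1.3, N = 73) and 3.3% (3/92, limited market release) from protocol 2.7; 1,250 to 1,550 subjects randomized 1:1 from SAP 8.5, which is 625 to 775 per arm.
- Check of the rates: 3/92 = 3.26%. The 2.7% fits 2/73 = 2.74%, where the count of 2 is inferred.
- Low end: 625 × 0.027 = 16.9.
- High end: 775 × 0.033 = 25.6.

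About 17 to 26 effusions of all kinds would be expected in the WaveCrest arm. For Version 1.3 the protocol reports: "Pericardial effusions/tamponade occurred at a rate of 2.7%, none requiring surgical intervention". A surgical-only item would have recorded none of those. With 0 of 73, the one-sided 95% upper bound is 1 − 0.05^(1/73) = 4.0%.

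**The case against.** The strongest reply is that this is a stray parenthesis and a loose definition, with nothing lost that matters. Drained effusions related to the procedure or device are in the primary safety composite, its components are tabulated through 45 days, tamponade is counted as major bleeding, and all adverse events are summarised. Both affected endpoints are descriptive, and SAP 8.7 says no labeling indication will be sought on them. All of that stands, and it is why the point is minor.

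The reply also notes that the protocol is consistent in counting surgical drainage only, which matches the possible benefit in section 3.2, so deleting the parenthesis would resolve the first conflict. That is correct as far as consistency goes. It would still leave no visible by-arm count of effusions drained by catheter, although the SAP's own display suggests that such a count was wanted.

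Three stronger readings are tempting, and the documents do not support them:
- *That a key procedural harm is under-reported.* The routes above capture drained procedure- or device-related effusions whatever their size.
- *That the surgical item will be near zero in both arms.* The only support is one WaveCrest group of 73, whose upper bound is 4.0%; section 2.7 gives no surgical-drainage rate for Watchman.
- *That a given number of small effusions will be lost per arm.* The documents give no share of effusions at 10 mm or less, and the available rates are for WaveCrest alone. Because the definition contradicts itself, they do not even settle that small effusions are excluded.

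**Conclusion.** Both inconsistencies are real and should be corrected, at minor severity. The drainage item cannot be presented as the SAP says. The effusion definition, applied literally, drops symptomatic or drained effusions of 10 mm or less while providing a size class for them. Any loss is confined to two descriptive results: the 7-day or discharge drainage item, and the effusion part of the 45-day stroke-or-effusion rate. No hypothesis, margin or success criterion changes.

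The conclusion rests on the visible text, on reading the opening threshold as a precondition, and on size and growth being measured in the same dimension. The figure of 17 to 26 effusions is for scale only. It assumes that the WaveCrest rates in protocol 2.7 carry over to this trial; it says nothing about the Watchman arm or about how many cases the wording would affect.

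**What to change.** Before unblinding:

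1. Align the synopsis, protocol 15.6 and SAP 8.7.1 so that the item reports effusions requiring percutaneous or surgical drainage through 7 days or discharge, shown by type. Keep the surgical count as its own row, so that the endpoint the protocol now names remains readable.
2. Reword Appendix I so that the threshold of more than 10 mm applies only to asymptomatic, undrained effusions. The growth criterion already does this, so removing the threshold from the opening clause would be enough. Check that the size classes match; *Mild* then becomes reachable.

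The cost is mainly a wording change in two documents. Much of the data is already collected: adverse events recorded at the procedure (protocol 6.3), the mandatory pre-discharge TTE (6.4) and core laboratory review (4.2). Descriptive effusion counts may rise slightly, and symptomatic or drained effusions of 10 mm or less already on record may need reclassifying. The adjudication committee's listed remit (protocol 18.2) does not name descriptive effusion events, so the sponsor should state who makes that classification.

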8.7.2 Descriptive Effectiveness Endpoints

Descriptive effectiveness endpoints will be summarized and presented as detailed below.

- **Primary effectiveness event rate at 6 months, 3 years, 4 years and 5 years**

After the primary analysis, primary effectiveness event rates will be estimated at 6 months, 3 years, 4 years and 5 years under the Bayesian piecewise exponential model. [REDACTED]

[REDACTED]

- **Composite of all stroke, systemic embolism, or TIA**

Event rates per subject-year for the composite of all stroke, systemic thromboembolism or TIA (as well as for each component) will be estimated assuming a one-parameter exponential survival model. [REDACTED]

- **Landmark analysis of primary effectiveness endpoint**

A landmark analysis of the primary effectiveness endpoint will be carried out with subject exposure start times beginning at the 45-day visit [REDACTED]

- **Landmark analysis of the incidence of ischemic stroke from 6 months following device implantation and discontinuation of oral anticoagulant and dual antiplatelet therapy**

Event rates per subject-year for ischemic stroke will be estimated assuming a one-parameter exponential survival model. [REDACTED]

- **Composite of all-cause stroke**

Event rates per subject-year for strokes of any etiology (ischemic, hemorrhagic, or other) will be estimated assuming a one-parameter exponential survival model. [REDACTED]

- **Incidence of thrombus formation on the left atrial surface of the implant**

Event rates of thrombus on the left atrial surface of the implant through all available follow-up based on TEE examination as reported by the Echocardiography Core Laboratory (ECL) will be summarized.

- **Strokes adjudicated as ischemic, hemorrhagic, or indeterminate**

Event rates per subject-year for ischemic, hemorrhagic, or indeterminate strokes will be estimated assuming a one-parameter exponential survival model. [REDACTED]

- **Strokes adjudicated as major or minor**

Event rates per subject-year for major and minor strokes will be estimated assuming a one-parameter exponential survival model. [REDACTED]

- **Strokes adjudicated as cardioembolic in origin**

Event rates per subject-year for cardioembolic strokes will be estimated assuming an exponential survival model. [REDACTED]
[REDACTED]

- **Freedom from oral anticoagulants**

The proportion of subjects free from oral anticoagulants after each scheduled follow-up visit will be summarized. [REDACTED]
[REDACTED]

- **Number of devices used per subject**

The number of devices used (i.e., attempted) will be summarized. The number of devices used will be summarized by the proportion of subjects in whom 0, 1, 2 or >2 devices were attempted. [REDACTED]
[REDACTED]

- **Procedural success**

The procedural success rate will be calculated as the proportion of subjects who experience successful placement and release of the occluder in the LAA with LAA closure (defined as no color flow Doppler flow > 5mm) and discharge from the cardiac catheterization laboratory without procedure-related complications [REDACTED]
[REDACTED]
[REDACTED]

- **Technical Success**

The technical success rate will be calculated as the proportion of subjects who experience successful placement and release of the occluder in the LAA with LAA closure (defined as no color flow Doppler flow > 5mm) and discharge from the cardiac catheterization laboratory without the occurrence of a device-related adverse event.

- **Device success**

Device success will be calculated as the proportion of subjects who have the device deployed and implanted in the correct position.

[figure not shown]
[figure not shown]
- **LAA closure rate at 45 days, 6 months, and 1 year**

LAA closure will be assessed in subjects whose 45-day, 6-month and 1-year TEEs have been evaluated by the Echocardiography Core Lab for residual leak/gap measurement. As defined in the protocol, LAA closure is defined as no residual leak or if leak is present, residual gap \leq 5mm. [REDACTED]
[REDACTED]
[REDACTED]

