Primary Safety Endpoint	
Composite rate of:
 
 
• All cause death; or
 
• Procedure- or device-related complications requiring percutaneous or surgical intervention through 45 days post-procedure; or
 
• Major bleeding
 

	Title: The WAVECREST 2 Trial  Clinical Investigational Plan	Doc. #: CHX_IP014	Rev: H
---	--	-----------------------------	------------------

Secondary Endpoints	
 
• Rate of ischemic stroke or systemic embolism with the WaveCrest device in comparison to the CHADS2 and CHA2DS2-VASc imputed risk of ischemic stroke or systemic embolism in the absence of anticoagulant therapy
 
• Rate of LAA closure (gap ≤ 5mm) at 45 days
 

Descriptive Safety Endpoints	
 
• Components of the composite primary safety endpoint through 45 days post-procedure
 
• The rates of stroke (all types) or pericardial effusion through 45 days post-procedure
 
• Pericardial effusion requiring surgical drainage through 7 days post-procedure or at hospital discharge, whichever is later
 
• Device- or procedure-related Serious Adverse Events (SAEs) reported by site at 45 days, 6 months, and at each annual follow-up period
 
• All-cause mortality 45 days, 6 months, and at each annual follow-up period
 
• Cardiovascular mortality at 45 days, 6 months, and at each annual follow-up period
 

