Descriptive Effectiveness Endpoints	
 
• Primary effectiveness endpoint event rate at 6 months, 1 year, 3 years, 4 years and 5 years
 
• Composite of all stroke, systemic thromboembolism, or TIA at 45 days, 6 months and at each annual follow-up period
 
• Landmark analysis of primary effectiveness endpoint from the 45-day visit to the time of each annual follow-up period
 
• Landmark analysis of the incidence of ischemic stroke from 6 months following device implantation and discontinuation of oral anticoagulant and dual antiplatelet therapy
 
• Composite of all-cause stroke at 45 days, 6 months, and at each annual follow-up period
 
• Incidence of thrombus on the surface of the device at 45 days, 1 year, and throughout all follow-up
 
• Strokes adjudicated as ischemic, hemorrhagic, or indeterminate at 45 days, 6 months, and at each annual follow-up period
 
• Strokes adjudicated as major or minor at 45 days, 6 months, and at each annual follow-up period
 
• Stroke adjudicated as cardioembolic in origin at 45 days, 6 months, and at each annual follow-up period
 
• Freedom from oral anticoagulants after each protocol-required follow-up visit
 
• Number of devices used per subject
 
• Procedural success
 

	Title: The WAVECREST 2 Trial  Clinical Investigational Plan	Doc. #: CHX_IP014	Rev: H
---	--	-----------------------------	------------------

	
 
• Technical success
 
• Device success
 
• LAA Closure as determined by Echocardiography Core Lab (ECL) at 45 days, 6 months, and at 1 year
 
• Procedure time, device duration, contrast volume used, and fluoroscopy time
 

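### Stroke and all-cause death are summarised by a single constant rate; the fitting window is not visible, and stroke alone has no visible model-free estimate at the protocol's time points

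*SAP*

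**What the plan says.** **Model.** SAP 8.7.2, on all-cause stroke: "Event rates per subject-year for strokes of any etiology (ischemic, hemorrhagic, or other) will be estimated assuming a one-parameter exponential survival model". The same one-parameter wording is used there for the composite of all stroke, systemic embolism or TIA and its components, for ischemic, hemorrhagic and indeterminate stroke, and for major and minor stroke. SAP 8.7.1, on death: "Event rates per subject-year for all-cause mortality will be estimated assuming a one-parameter exponential survival model". Two endpoints are worded more loosely: "Event rates per patient-year for cardiovascular mortality will be estimated assuming an exponential survival model" (8.7.1) and "Event rates per subject-year for cardioembolic strokes will be estimated assuming an exponential survival model" (8.7.2). Redacted text follows each of these model sentences.

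**Times.** The protocol Synopsis lists "Composite of all-cause stroke at 45 days, 6 months, and at each annual follow-up period", and section 15.6 repeats those times. The other stroke endpoints named above have the same schedule. For death the protocol gives two schedules. The Synopsis has "All-cause mortality 45 days, 6 months, and at each annual follow-up period". Section 15.6 has the primary analysis, each later annual period and 5 years, without 45 days or 6 months.

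**Primary endpoints.** Protocol 15.3 calculates the safety rate with a piecewise method (the rest is redacted). SAP 8.7.2 estimates the primary effectiveness rate at 6 months and at 3, 4 and 5 years "under the Bayesian piecewise exponential model".

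**Other early displays.** SAP 8.7.1 gives the number and percentage of subjects through 45 days for each primary safety component, which includes all-cause death. It does the same for stroke or pericardial effusion taken together.

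**The concern.** A one-parameter exponential has one hazard for the whole of follow-up. It can describe risk at several times only if the hazard is constant or the model is refitted for each time. The visible text says neither.

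There is reason to doubt a constant hazard after an implant. The primary endpoints are modelled piecewise, and landmark analyses restart the clock at 45 days and at 6 months. Protocol 3.3 lists stroke among the procedural risks. Protocol Table 3 changes antithrombotic treatment at different times in the two arms.

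If risk is front-loaded, a single rate averages the procedural period with the later period, and its value depends on how long subjects were followed. A reader who wants 45-day or 6-month stroke risk by arm could then be misled. At 6 months there is also a possible inconsistency: the stroke/embolism/TIA composite contains the primary effectiveness event, yet a pooled constant-rate figure for the composite could fall below the piecewise figure for the event inside it.

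**Working it through.** The plan gives no figure for these endpoints, so there is none to reproduce. The check asks what a one-rate fit returns when the hazard is higher in the first 45 days.

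**Example 1 (assumed inputs, not in the documents).** Risk of 1% in the first 45 days, then 0.015 per year; complete follow-up to time T.

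- t0 = 45/365 = 0.1233 years. Early hazard h = -ln(0.99)/0.1233 = 0.0815 per year, about 5.4 times the later hazard.
- Expected events per subject by T: 1 - 0.99 × exp(-0.015 × (T - t0)). At T = 2 this is 0.0375.
- Expected person-years by T: 0.01/h + 0.99 × (1 - exp(-0.015 × (T - t0)))/0.015. At T = 2 this is 0.1227 + 1.8320 = 1.9547.
- Fitted rate = 0.03748/1.9547 = 1.92 per 100 patient-years.
- Implied 45-day risk = 1 - exp(-0.01918 × 0.1233) = 0.24%, against a true 1%.
- Implied 6-month risk = 0.95%, against a true 1.56%.

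With 2% early risk the 24-month rate is 2.44. It implies 0.30% at 45 days (true 2%) and 1.21% at 6 months (true 2.55%).

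**Example 2 (later hazard tied to the protocol).** Protocol 2.6 reports 0.0253 at 18 months for ischemic stroke or systemic embolism beyond 7 days in the device arm of the second Watchman trial. Read as an 18-month risk, this gives -ln(1 - 0.0253)/1.5 = 0.017 per year. A second value, 0.03 per year, was also run. The early hazard multiple k is assumed. For one rate fitted over 2 years at 0.017 per year:

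| k | 45-day risk, implied v true | Ratio | 6-month risk, implied v true |
|---|---|---|---|
| 1 | 0.21% v 0.21% | 1.00 | 0.85% v 0.85% |
| 2 | 0.22% v 0.42% | 0.53 | 0.90% v 1.05% |
| 5 | 0.26% v 1.04% | 0.25 | 1.06% v 1.67% |
| 10 | 0.33% v 2.07% | 0.16 | 1.32% v 2.70% |

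The 45-day ratios are the same at 0.03 per year. With a constant hazard (k = 1) there is no bias. Risk at the end of the fitting window is almost unaffected: at 2 years with k = 5, 4.17% against 4.15%.

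**If the model is refitted to follow-up cut at each time.** The 45-day risk is then exact for every k. The 6-month risk is nearly so: with k = 10, 2.72% against 2.70% at 0.017 per year, and 4.77% against 4.71% at 0.03 per year.

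**What refitting does not cure.** The stated output is a rate per subject-year. In the 1% example:

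| Window | Events per subject | Person-years | Rate per 100 patient-years |
|---|---|---|---|
| 6 months | 0.0156 | 0.4946 | 3.15 |
| 1 year | 0.0229 | 0.9849 | 2.33 |
| 2 years | 0.0375 | 1.9547 | 1.92 |
| 5 years | 0.0798 | 4.7783 | 1.67 |

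The hazard after day 45 is 1.5 per 100 patient-years throughout. The fall comes only from the longer denominator.

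**The case against.** A reader might infer that the plan will understate early stroke and death. The documents do not support that, for these reasons:

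- The fitting window may lie in the redacted text. Reporting at several times is compatible with separate fits, which remove the 45-day error.
- The visible SAP promises rates per subject-year. It nowhere says that a pooled rate will be converted to a 45-day or 6-month risk; that conversion is made here.
- The early hazard is assumed. The documents attribute the excess of Watchman safety events mainly to peri-procedural complications, but give no early hazard for stroke or death. Protocol 2.7 reports no procedural strokes in the WaveCrest limited market release.
- Deaths through 45 days are tabulated without a model, and the landmark analyses separate later from early events.

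A reader might also infer that all-stroke risk at 45 days would come out below a piecewise ischemic-stroke risk at 45 days. No 45-day piecewise output is visibly planned, and the piecewise endpoint is ischemic stroke or systemic embolism. The inconsistency is possible at 6 months, and only with a pooled fit.

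Finally, extending the one-parameter criticism to cardiovascular death and cardioembolic stroke goes beyond the text, which calls those models only exponential.

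All of this stands and limits the point. Two things are left. A rate per subject-year moves with the window whenever risk is front-loaded, even with separate fits. And the visible plan shows 45-day stroke only together with pericardial effusion, with no model-free estimate of stroke alone, or by type or severity, at the times the protocol names.

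**Conclusion.** The point holds as a minor, conditional one. A constant-hazard rate per subject-year is a weak summary for endpoints requested at 45 days, 6 months and yearly.

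If one rate is pooled over 2 years, the implied 45-day risk would be 53%, 25% or 16% of the true value for early hazards 2, 5 or 10 times the later one. If follow-up is cut at each time, the 45-day risk is right and only the drift of the rate remains. With a constant hazard neither problem arises. Which case applies cannot be seen, and the early multiples are assumptions, so no actual bias is established.

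The point is mainly about stroke, because early all-cause death already has its count and percentage. These endpoints are descriptive, SAP 8.7 says no labeling claim will be sought on them, and trial success does not depend on them.

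**What to change.** In SAP 8.7.1 and 8.7.2:

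1. For the stroke endpoints, report cumulative incidence by arm at 45 days, 6 months and each year, with death as a competing event. Show stroke alone at 45 days, separate from pericardial effusion.
2. For all-cause death, report Kaplan-Meier estimates by arm at the protocol's times, after reconciling the Synopsis schedule with protocol section 15.6.
3. Keep the per-subject-year rate as a secondary display and state the follow-up window it is fitted to.
4. Say whether the exponential models for cardiovascular death and cardioembolic stroke have one parameter.

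The cost is a little more programming for standard output. No new data are needed, and the primary analyses and sample size do not change.
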